#### **7.6.1.2 Ophthalmological Exam and Eye Examination Data**

The data for ophthalmological exam and eye examination at baseline and other applicable visits will be listed. Summary statistics of ophthalmological exam and eye examination results will be tabulated by visit where appropriate. Shift tables comparing the worst post-baseline to baseline results will be presented. Summaries may include but are not limited to

visual acuity, Schirmer's test, slit lamp test, conjunctivas and corneas including staining, intraocular pressure, and fundoscopy.

### **7.6.2 Clinical Laboratory Parameters**

All laboratory results up to the end of treatment visit will be presented in standardized units. Grading of laboratory values will be assigned programmatically per the NCI CTCAE. Summary statistics of selected laboratory results (complete blood count with differential, serum chemistry, and coagulation panel) and changes from baseline will be tabulated by scheduled visit. The highest post-baseline grade will be presented for each lab test. Shift tables comparing the highest post-baseline to baseline CTCAE grade will be presented based on number of subjects in safety analysis set with a baseline and at least one post-baseline laboratory value.

In addition, clinical laboratory data may be presented graphically for selected lab tests, by scheduled visit.

Laboratory values will be listed with grade per CTCAE and flagged when values are outside the normal reference range.

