3 INVESTIGATIONAL PLAN

3.1 Summary of Study Design

This is an open-label, phase 2 study with an initial safety run-in period. The safety run-in period will evaluate the safety of a dose-dense schedule and will start at a 0.9 mg/kg dose level. If 0.9 mg/kg is considered safe and tolerable, the dose level will be escalated to 1.2 mg/kg. Otherwise it will be de-escalated to 0.65 mg/kg. Each dose level will enroll approximately 6 patients. Patients who do not complete the DLT period will be replaced. A

dose level is considered safe and tolerable if no more than 1 patient experiences a DLT among 6 patients during the DLT period. The highest dose level that is considered safe will be the recommended phase 2 dose (RP2D) and will be used in Part A. If no RP2D for the dose-dense schedule is identified, Part A will be a single arm of the Q3W regimen and Part B will not enroll.

In Part A, 60 patients will be randomized in a 1:1 ratio to receive tisotumab vedotin 2.0 mg/kg intravenously (IV) every 3 weeks (Q3W regimen) or the safety run-in RP2D on Days 1, 8, and 15 of every 4-week cycle (dose-dense regimen; 3Q4W) if a RP2D has been identified. Randomization will be stratified by first line vs. second line PROC and histology (serous vs. non-serous).

Based upon antitumor activity and safety data, one Part A treatment arm may be expanded to enroll up to an additional 70 patients to further characterize safety and antitumor activity of tisotumab vedotin for patients with PROC. The analysis to support expansion will be conducted when approximately 30 patients per arm have at least one post-baseline response assessment per RECIST v1.1 or have discontinued from the study or started subsequent cancer therapy.

Part B will enroll approximately 80 patients with PROC including approximately 60 patients who have received 1 to 3 prior lines of therapy, including bevacizumab treatment. Part B will further characterize the long-term efficacy, safety, and PK assessments of 0.9 mg/kg tisotumab vedotin on Days 1, 8, and 15 of every 4-week cycle (dose-dense regimen) if the 0.9 mg/kg dose level is considered safe and tolerable in the safety run-in period. Enrollment in this cohort may discontinue when Part A begins enrollment.

[figure not shown]

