6.3 Treatment Period (Q3W Regimen only)

6.3.1 Day 1 (± 1 day), All treatment cycles (exceptions noted)

- Cycle 1 only: Prior to dosing, confirm patient eligibility per inclusion/exclusion criteria
- Weight
- Physical Exam
- Predose vital signs
- ECOG Performance status (If Baseline Visit activities occur within 1 day prior, this assessment does not need to be repeated at Cycle 1, Day 1)
- Chemistry panel (results to be submitted to central laboratory; if Baseline Visit activities occur within 1 day prior, this assessment does not need to be repeated at Cycle 1, Day 1)
- CBC with differential (results to be submitted to central laboratory; if Baseline Visit activities occur within 1 day prior, this assessment does not need to be repeated at Cycle 1, Day 1)
- Pregnancy test for patients of childbearing potential (If Baseline Visit activities occur within 1 day prior, this assessment does not need to be repeated at Cycle 1, Day 1)
- Coagulation parameters (fibrinogen, INR, PT, and aPTT) (results to be submitted to central laboratory; if Baseline Visit activities occur within 1 day prior, this assessment does not need to be repeated at Cycle 1, Day 1)
- Eye exam performed by investigator
- Predose blood sample for PK evaluation (within 24 hours) (Cycles 1, 2, 3, 4, 5, and every other cycle thereafter)
- Predose blood sample for antitherapeutic antibody (ATA) evaluation (within 24 hours) (Cycles 1, 2, 3, 4, 5, and every other cycle thereafter)
- Predose blood sample for plasma proteomic analysis (within 24 hours) (Cycles 1, 2, 3, 4, 5, and every other cycle thereafter)
- Predose blood sample for plasma mutational analysis (within 24 hours) (Cycles 1, 2, 3, 4, 5, and every other cycle thereafter)
- Predose blood sample for plasma exosome analysis (within 24 hours) (Cycles 1, 2, 3, 4, 5, and every other cycle thereafter)
- Predose blood sample for PBMC immune subsets analysis (within 24 hours) (Cycles 1, 2, 3, and 4 only)
- Ocular premedication and preventative eye therapy (see Section 5.4 and [Appendix C](#))
- Ensure patient completes dosing diary
- Parts A and B, US patients only: Patient-reported outcomes questionnaires (all questions). If Baseline Visit activities occur within 1 day prior, this assessment does not need to be repeated at Cycle 1, Day 1.
- Tisotumab vedotin administration

- Blood samples for PK evaluation (all time points from end of infusion)
 - End of infusion (+ 15 minutes) (Cycles 1, 2, 3, 4, 5, and every other cycle thereafter)

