6.3.4 Cycle 1 Day 8 (\pm 1 day)

- CBC with differential (results to be submitted to central laboratory)
- Chemistry panel (results to be submitted to central laboratory)
- Coagulation parameters (fibrinogen, INR, PT, and aPTT) (results to be submitted to central laboratory)
- Eye exam performed by investigator
- Blood sample for PK evaluation (168 hours \pm 24 hours after the end of infusion)
- Blood sample for plasma proteomic analysis (168 hours \pm 24 hours after the end of infusion)
- Parts A and B, US patients only: PRO-CTCAE patient-reported outcomes questionnaire

6.3.5 Cycle 1 and 2, Day 15

- Blood sample for PK evaluation (336 hours \pm 24 hours after the end of infusion)
- Blood sample for plasma proteomic analysis (336 hours \pm 24 hours after the end of infusion)
- Parts A and B, US patients only: PRO-CTCAE patient-reported outcomes questionnaire

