6.3.6 Cycle 2, Day 8 (± 1 day)

- Blood sample for PK evaluation (168 hours ± 24 hours after the end of infusion)
- Blood sample for plasma proteomic analysis (168 hours ± 24 hours after the end of infusion)
- Parts A and B, US patients only: PRO-CTCAE patient-reported outcomes questionnaire

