6.4.4 All Treatment Cycles, Day 8 (\pm 1 day) (Exceptions Noted)

- Weight
- Physical Exam
- Predose vital signs
- Chemistry panel (results to be submitted to central laboratory)
- CBC with differential (results to be submitted to central laboratory)
- Coagulation parameters (fibrinogen, INR, PT, and aPTT) (results to be submitted to central laboratory)
- Eye exam performed by investigator
- Ocular premedication and preventative eye therapy (see Section 5.4 and Appendix C)
- Predose blood sample for PK evaluation (within 8 hours) (Cycles 1 and 2 only)
- Predose blood sample for plasma proteomic analysis (within 8 hours) (Cycles 1 and 2 only)
- Ensure patient completes dosing diary

- Parts A and B, US patients only: PRO-CTCAE patient-reported outcomes questionnaire
- Tisotumab vedotin administration

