7.7.8.2 Procedures for Eliciting and Recording Adverse Events

Eliciting Adverse Events

An open-ended or non-directed method of questioning should be used at each study visit to elicit the reporting of AEs.

Recording Adverse Events

The following information should be recorded on the Adverse Events and Pre-existing Conditions CRF:

- Description including onset and resolution dates
- Whether it met SAE criteria
- Severity
- Relationship to study treatment or other causality
- Outcome

Diagnosis vs. Signs or Symptoms

In general, the use of a unifying diagnosis is preferred to the listing out of individual symptoms. Grouping of symptoms into a diagnosis should only be done if each component sign and/or symptom is a medically confirmed component of a diagnosis as evidenced by standard medical textbooks. If any aspect of a sign or symptom does not fit into a classic pattern of the diagnosis, report the individual symptom as a separate adverse event.

Important exceptions for this study are adverse reactions associated with the infusion of study drug. For IRRs, do not use the NCI CTCAE terms of “cytokine release syndrome,”

“acute infusion reaction,” or “allergic or hypersensitivity reaction.” Instead, record each sign or symptom as an individual AE. If multiple signs or symptoms occur with a given infusion-related event, each sign or symptom should be recorded separately with its level of severity.

Recording Serious Adverse Events

For SAEs, record the event(s) on both the CRF and an SAE form.

The following should be considered when recording SAEs:

- Death is an outcome of an event. The event that resulted in the death should be recorded and reported on both an SAE form and CRF.
- For hospitalizations, surgical, or diagnostic procedures, the illness leading to the surgical or diagnostic procedure should be recorded as the SAE, not the procedure itself. The procedure should be captured in the narrative as part of the action taken in response to the illness.

Progression of the Underlying Malignancy

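### In Part A, worst-grade lab and investigator eye-exam summaries are not like-for-like between arms: scheduled looks run at 0.75 per week on dose-dense and 0.33 on Q3W in steady state

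*SAP*

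**What the plan says.** **Q3W arm.** Labs (CBC, chemistry, coagulation) and the investigator's eye exam are listed under Protocol "6.3.1 Day 1 (± 1 day), All treatment cycles (exceptions noted") and once more under "6.3.4 Cycle 1 Day 8". Section 6.3.6 (Cycle 2 Day 8) lists "Blood sample for PK evaluation", a proteomic sample and the US questionnaire, with no safety labs or eye exam. Section 6.3.5 (Day 15 of Cycles 1 and 2) is the same. Appendix C limits the Q3W Day 8 eye exam to Cycle 1.

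**Dose-dense arm.** The same labs and eye exam are listed on Day 1 (6.4.1), under "6.4.4 All Treatment Cycles, Day 8", and on Day 15 (6.4.5), in all cycles.

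**Analysis.** SAP 7.6 presents all safety analyses by cohort and total. SAP 7.6.2 uses results up to the end-of-treatment visit, reports the highest post-baseline grade for each test, and adds that "Shift tables comparing the highest post-baseline to baseline CTCAE grade will be presented". SAP 7.6.1.2 says of the eye data: "Shift tables comparing the worst post-baseline to baseline results will be presented". Neither section provides a matched-visit table or any allowance for the different schedules.

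**Use.** Protocol 3.2.1 says randomisation is meant to support evaluation of the safety and activity of the two schedules. Protocol 3.1 says: "Based upon antitumor activity and safety data, one Part A treatment arm may be expanded".

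**The concern.** A worst post-baseline value is a maximum over however many times the patient was examined. If one arm is examined more often, its maximum tends to be worse even when true toxicity is the same. A short-lived, symptom-free abnormality is exposed to this most, because a scheduled look may be the only way it is found. Anyone reading the two Part A columns side by side would then be seeing toxicity and frequency of observation mixed together. That matters because comparing the schedules is the stated reason for randomising, and one arm may be taken forward.

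**Working it through.** **1. Check of the visit pattern against the plan's own figures.** Protocol 3.2.2 gives dose intensities of 0.67 and 0.68 mg/kg/week; SAP 7.4 gives 0.667 and 0.675. From the schedule, 2.0 × 1/3 = 0.667 and 0.9 × 3/4 = 0.675. These agree and confirm one dosing visit per 3 weeks against three per 4 weeks.

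**2. Steady-state rate of scheduled labs and investigator eye exams.** Q3W: 1/3 = 0.33 per week. Dose-dense: 3/4 = 0.75 per week. Ratio: 0.75/0.333 = 2.25.

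**3. Count of scheduled post-baseline looks.** Cycle 1 Day 1 predose is baseline. The end-of-treatment visit adds one look in each arm and is left out. Patients are assumed to be on drug and on schedule.

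- Q3W: Days 8, 22, 43, 64, 85, ...
- Dose-dense: Days 8, 15, 29, 36, 43, 57, 64, 71, 85, ...

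| Through | Q3W | Dose-dense | Ratio |
|---|---|---|---|
| Week 4 (Day 28) | 2 | 2 | 1.0 |
| Day 43 | 3 | 5 | 1.7 |
| Day 85 | 5 | 9 | 1.8 |

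**4. What this could do to detection.** The documents give no durations, so the following is an illustration. Suppose an abnormality is found only at a scheduled look, starts at a random time in the first 42 days, and lasts an exponential time with mean D days, equally in both arms. The chance that it is still present at the next look is

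P = Σ (D/42)(1 − exp(−L/D)), summed over the gaps L between looks.

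The gaps to Day 43 are 7, 14, 21 for Q3W and 7, 7, 14, 7, 7 for dose-dense.

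- D = 7: Q3W (0.632 + 0.865 + 0.950)/6 = 41%; dose-dense (4 × 0.632 + 0.865)/6 = 57%.
- D = 14: Q3W (0.393 + 0.632 + 0.777)/3 = 60%; dose-dense (4 × 0.393 + 0.632)/3 = 74%.
- D = 28: Q3W (0.221 + 0.393 + 0.528) × 28/42 = 76%; dose-dense (4 × 0.221 + 0.393) × 28/42 = 85%.

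Relative to dose-dense, Q3W misses about 28%, 18% and 11%. An abnormality that lasts a fixed 21 days or more is caught in both arms, since no gap exceeds 21 days.

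**5. Days scheduled in both arms.** Days 8, 43, 64 and 85, then 127, 148 and 169. Days since the last dose (Q3W vs dose-dense) are 7 vs 7 on Day 8, 21 vs 7 on Days 43 and 64, and 21 vs 14 on Day 85.

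**The case against.** Several stronger readings are tempting, and the documents do not support them.

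- **That the expansion choice itself is biased.** No section says these tables feed that decision. The safety condition in Protocol 9.1 and SAP 6.2 is that a cohort's profile be acceptable, alongside activity criteria. The study has no formal hypothesis testing. The link is an inference.
- **That adverse event incidence is equally distorted.** Protocol 7.7.8.2 states: "An open-ended or non-directed method of questioning should be used at each study visit to elicit the reporting of AEs". Leaving out Day 2 in both arms, scheduled visits to Day 43 number 8 on Q3W (Days 3, 8, 15, 22, 24, 29, 36, 43) and 9 on dose-dense (Days 3, 8, 15, 17, 22, 29, 31, 36, 43), which is near parity. US patients in both arms complete PRO-CTCAE weekly. Symptom-free lab values are generally not recorded as adverse events (7.7.8.1).
- **That all eye data are affected.** The tests named in SAP 7.6.1.2 (acuity, Schirmer, slit lamp, staining, pressure, fundoscopy) are ophthalmologist tests, scheduled only at screening in both arms (Protocol 7.7.4). Only the investigator's inspection differs in scheduled frequency, although its findings do prompt referral (7.7.5).
- **That Q3W samples are taken after recovery and dose-dense samples near the nadir.** Neither document gives a nadir or a recovery time.
- **That Q3W misses 40%, 27% and 16%.** Those figures come from applying the steady-state 21-day gap throughout, which ignores Cycle 1 Day 8. They do not describe the first six weeks, when the expansion analysis can begin.

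Two further points stand. More looks can lead to earlier dose holds (Protocol 5.3), which could lower the worst grade on dose-dense. The SAP also tabulates results by scheduled visit, so some same-day comparison is already possible. It is limited, however: the same visit label falls on different days after Cycle 1 (Cycle 2 Day 1 is Day 22 on Q3W and Day 29 on dose-dense), and by-visit means do not replace a worst-grade table.

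**Conclusion.** The concern holds for the worst-grade lab tables and the investigator eye-exam summaries in Part A. They are not like-for-like between the randomised arms, and for transient, symptom-free findings they tend to disfavour dose-dense. The difference in looks is a matter of counting: none through Week 4, 5 vs 3 by Day 43, 9 vs 5 by Day 85, and 2.25-fold in steady state. Its effect on the tables cannot be computed from the documents. The 11% to 28% relative miss to Day 43 rests on assumed durations, equal true toxicity and treatment on schedule. The direction is likely but not proven. A reader should not go on to conclude that the expansion decision is biased or that adverse event rates are equally affected. This is a cheap improvement to a descriptive safety comparison and does not make the planned tables invalid.

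**What to change.** In SAP 7.6.1.2 and 7.6.2, for the Part A randomised arms, add a supplementary worst-grade or shift table restricted to study days scheduled in both arms: Days 8, 43, 64, 85 and onward. State the window around each day, since dose delays will move visits. Read this table alongside the all-assessments table whenever the two arms' safety is compared, including at expansion.

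It should not replace the full table. By Day 43 it would drop three of the five dose-dense looks (Days 15, 29 and 36), for a schedule on which Protocol 1.3.3.1 reports Grade 3 or higher ocular events in 6 of 26 patients (23%) at 1.2 mg/kg.

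The cost is one extra set of tables, with no change to visits or procedures. The limitation should be stated with the table: it uses fewer data, and time since last dose still differs between arms on every common day except Day 8. It therefore equalises the number of looks but not their timing relative to dosing.

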### **7.6.3 Deaths**

The number of total deaths, deaths that occur within 30 days of last study treatment, and deaths that occur more than 30 days after last study treatment as well as the relationship to disease will be summarized. In addition, cause of death will be displayed in MedDRA preferred term (unless otherwise specified) and summarized. Death information will be listed by patient.

### **7.6.4 Concomitant Medications**

Concomitant medications will be summarized by the World Health Organization (WHO) drug substance name. The number and percentage of patients taking concomitant medications will be tabulated for the following, but not limited to:

- Ocular premedication and preventive eye therapy which include ocular vasoconstrictor eye drops, eye cooling pads, steroid eye drops, and lubricating eye drops
- Anti-coagulation therapy if applicable
- Granulocyte-Colony Stimulating Factor (G-CSF)

Concomitant medications will be listed by patient.

### **7.6.5 Other Safety Analyses**

#### **7.6.5.1 Vital Signs**

Vital sign data will be listed by patient for each time point. Summary statistics of vital signs and change from baseline may be tabulated where appropriate.

### **7.6.5.2 ECOG Performance Status**

ECOG performance status will be summarized for each visit. Shifts from baseline to the lowest and highest post-baseline score will be tabulated.

### **7.6.5.3 ECG**

ECG status (normal, abnormal clinically significant, or abnormal not clinically significant) will be summarized by scheduled visit, and shifts from baseline will be tabulated.

## **7.7 Additional Analyses**

### **7.7.1 Pharmacokinetics**

Tisotumab vedotin antibody drug conjugate (ADC), total antibody (TAb), and MMAE concentrations will be summarized with descriptive statistics at each PK sampling time point. Selected PK parameters for ADC, TAb, and MMAE will be estimated by noncompartmental analysis (NCA) and summarized using descriptive statistics. The PK parameters will be tabulated using the PK analysis set which includes enrolled patients who received any amount of study drug and at least one PK parameter can be estimated. Data from this study may be combined with PK data from other clinical trials with tisotumab vedotin for population PK and PK/pharmacodynamic analyses.

### **7.7.2 Antitherapeutic Antibody (ATA)**

The ATA incidence rate is defined as the proportion of patients who develop ATA at any time during the study. The ATA incidence rate will be summarized by cohort and total using the safety analysis set.

### **7.7.3 Biomarkers**

Relationships of biomarker parameters (e.g., baseline values, absolute and relative changes from baseline) to efficacy, safety, and pharmacokinetic parameters will be explored. Relationships and associated data that are determined to be of interest will be summarized. Details will be described separately in the Biomarker Analysis Plan.

### **7.7.4 Patient Reported Outcomes Analyses**

Patient reported outcomes (PRO) as measured by NCI PRO-CTCAE and PROMIS will be summarized over time with descriptive statistics by visit using the FAS. For PRO-CTCAE, number and proportion of patients who experience a symptom with score  $>0$  and with score of 3 or 4 will be summarized by symptom and visit. Shift tables comparing the highest post-baseline score to baseline score will be presented by symptom. Missing data will be summarized with the proportion of patients missing responses for each question.

The PROMIS Physical Function Scoring Manual will be used to calculate T-score and to impute missing data. The T-score and change from baseline will be summarized by visit. The number of missing questions at each visit will be summarized.

The compliance and completion rate of NCI PRO-CTCAE and PROMIS will be summarized for each assessment time point. Compliance rate is defined as the proportion of patients who completed the instrument among those who are expected to complete at a given visit.

Completion rate is defined as the proportion of patients who completed the instrument among the FAS analysis set.

## 8 INTERIM ANALYSIS

A safety analysis will be conducted 28 days after all patients at the 0.9 mg/kg dose level in the safety run-in portion have received at least one dose of study treatment to evaluate the tolerability of the dose-dense regimen. If applicable, a second safety analysis will be conducted 28 days after all patients at the 1.2 mg/kg dose level have received at least one dose of study treatment. A safety monitoring committee (SMC), consisting of the investigators, study medical monitor, biostatistician, and drug safety representative, will review the safety data before proceeding to Parts A and B.

Interim analysis for futility will be performed on Part B after at least 20 patients with 1 to 3 prior lines of therapy, including bevacizumab treatment, have been treated and had at least one response assessment post-baseline.

The Bayesian predictive probability approach will be used to assess the futility criteria (Lee 2008). At the time of the interim futility analysis, the PPoS will be calculated. PPoS is the probability of achieving “success” should the cohort be continued to the maximum sample size of 60 in the target population (1 to 3 prior lines of therapy, including bevacizumab treatment) given the data observed at interim, and the cohort is considered “success” if the posterior probability that the ORR exceeds the response rate of current standard of care (i.e., 12% as reference in Section 3.2) is greater than 70%.

Both the confirmed and unconfirmed CR or PR observed at interim will be counted as a response for the calculation of PPoS. It is appropriate to include the unconfirmed response for the purpose of interim analysis because based on the estimates from GEN701 trial, about 60% of the responders will respond at their first post-baseline scan and approximately 75% of the confirmed/unconfirmed responses will eventually be confirmed. Table 1 summarizes the PPoS based on the number of responses observed among the first 20 patients.

